Qsymia Study

Principal Investigator: [name]

Investigators: [name]; [name], NP

Study Manager: [name], MS

NCT02301416

Scientific Basis/Rationale

While there is obvious focus on the obesity epidemic that affects approximately one-third of the U.S. population, one subgroup within the epidemic remains on the fringe of scientific study and effective treatment options. The super obese patient, in this instance defined as those with a BMI ≥ 50 kg/m², presents a difficult treatment challenge in managing this level of obesity. While bariatric surgery, including Roux-en-Y gastric bypass and biliopancreatic diversion with duodenal switch, have been shown to be effective in severe obesity (BMI ≥ 40 kg/m²), the risks involved with surgical intervention in the super obese patient are high. Perioperative morbidity is significantly higher, and mortality is as high as 5.2% at 1 year in some series (Nguyen et al, 2012). To address this issue, surgeons are offering patients a two-stage weight loss process that involves an initial laparoscopic sleeve gastrectomy, followed by the laparoscopic Roux-en-Y gastric bypass after initial weight loss. Some case series have reported improved morbidity and perioperative mortality similar to patients that are in lower BMI categories. A subset of patients using this approach will however not require the second surgery due to success with the first procedure. Alexandrou et al estimated that approximately 30% of patients lost sufficient weight to not require the second procedure in their experience (Alexandrou et al., 2012). Treatment plans that limit the need for the second procedure by promoting effective pre-operative and post-operative weight reduction as an adjunct to the surgical intervention would be valuable. These types of treatment plans would be valuable because they would decrease risk for the patient by eliminating the need for a second surgical procedure and there would be a reduction in cost for the patient and insurer/health system.

Qsymia provides a potential opportunity to develop an effective treatment plan that would be an adjunct to surgical intervention in the super obese patient. Use of Qsymia in addition to a low-calorie dietary prescription pre-operatively would effectively decrease weight prior to surgical intervention, lowering surgical risk to some extent. Additionally, if continued post-operatively, Qsymia as an adjunct to the post-surgical dietary plan would potentially extend the weight loss horizon so that the probability of the typical weight loss plateau at 12-18 months is decreased. The combination of the pre-operative and post-operative weight loss associated with Qsymia use could significantly diminish the need for a second surgical procedure in super obese patients. We have designed a pilot study to examine the use of Qsymia in super obese patients to determine its potential for decreasing the need for a second weight loss surgery.

Primary Objective

The primary objective of the proposed study is to demonstrate the effectiveness of using Qsymia in the superobese (BMI ≥ 50 kg/m²) as an adjunct to surgical therapy.

Secondary Objectives

Secondary objectives of the proposed study include determining tolerability of Qsymia perioperatively, determining changes in resting metabolic rate postoperatively (3 months and 12 months post-surgery), determining the magnitude of preoperative weight loss and determining the magnitude of weight loss at 12, 18, and 24 months post-surgery.

Treatment Plan

Treatment Group

Patients with a BMI ≥ 50 kg/m² that agree to participate in the experimental group will begin their treatment plan with a medical weight loss diet that includes a low-calorie diet and Qsymia at the recommended treatment dose of 7.5/46 mg daily (following initiation of the titration dose for 2 weeks). The low-calorie diet will be individually tailored based on initial resting metabolic rate measurement and co-morbid conditions. Patients will be medically monitored with once monthly medical visits and also have once monthly visits with a dietitian to review the treatment plan. Patients will receive medical weight loss therapy for a minimum of 3 months prior to proceeding to the laparoscopic sleeve gastrectomy. If a patient opts not to proceed to sleeve gastrectomy, they will continue to receive medical therapy for weight reduction including Qsymia and followed for the duration of the study (i.e., for 2 years).

Patients will discontinue Qsymia the week prior to the scheduled operation. The sleeve gastrectomy will be performed by one of the surgeons at the Weight Management Center ([name], [name], [name]) using standard laparoscopic technique. Post-operatively, all patients will be provided with dietary counseling and a nutrition prescription for a very low calorie, high protein diet: 500-700 calories, protein goal of 1-1.2g/kg IBW, and 60-75g carbohydrate. Qsymia will be resumed in the second post-operative week at the initial titration dose and increased to the recommended treatment dose of 7.5/46 mg daily. Patients will have standard post-operative surgical follow up at months 1, 3, 6, 9, 12, 18, and 24. During the post-operative phase, all patients will be enrolled in the bariatric support group program that meets on a monthly basis. Patients will also have at least 3 visits with a clinic dietitian to review and update dietary prescriptions. At any point during this course of follow up, a determination can be made that the primary outcome event has occurred if the patient has a weight plateau—defined as weight gain or < 3 lbs weight loss—for 3 consecutive months, remains above a BMI of 39.9 kg/m² and continues to have associated co-morbidities. These patients will be evaluated for the possibility of moving forward to the next operative stage (laparoscopic Roux-en-Y gastric bypass) while all other patients will continue on with medication and diet/exercise therapy.

Control Group

Control subjects for the proposed study will be identified from the patient population at the Wake Forest Baptist Health Weight Management Center. They will be matched to subjects in the treatment group on age, sex, ethnicity, and BMI. They will be a historical control group who had surgery prior to the commencement of the proposed study (retrospective review).

Trial Design

Prospective independent historical case control

Inclusion Criteria

Inclusion criteria for the proposed study are:

- BMI \geq 50 kg/m²
- Determined to be a good candidate for surgery based on medical and psychological exam.
- Willing to participate in a 3-6 month medically supervised weight loss plan prior to surgery.
- Planning to remain in the reasonable vicinity of the Wake Forest Baptist Health Weight Management Center for the duration of the study.

Exclusion Criteria

- History of prior weight loss surgery (removal/conversion from band to sleeve will not be excluded)
- Pregnant (women of childbearing potential will complete a pregnancy test (blood draw) to make sure they are not pregnant at the time that they initiate the medication). Ongoing monitoring of pregnancy status is the responsibility of the patient and they are instructed as such in the consent form.
- Ongoing use of weight loss medication
- Contraindications to use of Qsymia, including pregnancy, history of glaucoma, unstable cardiac disease (unstable angina, recent heart attack or stroke (in the past 6 months), uncontrolled arrhythmia), hyperthyroidism, taking MAOIs (monoamine oxidase inhibitors) or allergy to either topiramate or sympathomimetic amines like phentermine.

Patients may be removed from the study at any point if they are unable to tolerate the study medication or are less than 50% compliant with the study medication (take less than 50% of the recommended dose). If a patient is removed from the study due to medication intolerance or non-compliance, the study physician will meet with them and instruct them on how to stop the medication.

Primary endpoint

The primary endpoint for this study is the proportion of patients that meet the criteria to move forward with the second surgical procedure (Roux en Y Gastric Bypass). The criteria include all of the following at any point in the 24 month post-surgical follow up period:

1. Weight plateau (defined as weight gain or < 3 lbs weight loss) for at least 3 months
2. Remains above a BMI of 39.9 kg/m²
3. Continues to have obesity associated co-morbidities (Co-morbidities include hypertension, type 2 diabetes mellitus or pre-diabetes, hyperlipidemia, metabolic syndrome, obstructive sleep apnea, osteoarthritis, non-alcoholic steatohepatitis (NASH), gastroesophageal reflux disease (GERD)).

We hypothesize that the study group treated with Qsymia plus surgery will have a lower rate of occurrence of the primary endpoint at 24 months post-surgery compared to the group with surgery only.

Secondary endpoints

The secondary endpoints for this study are percent weight loss both before and after surgery and changes in percent body fat and resting metabolic rate.

We hypothesize that the study group treated with Qsymia plus surgery will have greater percent weight loss at all time points compared to the group treated with surgery only. We also hypothesize that the study group treated with Qsymia plus surgery will have a higher resting metabolic rate after adjustment for lean body mass compared to the group treated with surgery only.

Other measures obtained by chart review

Height will be measured at all new patient visits and will be repeated at 24 months to account for any changes over the course of participation. Weight is measured at every clinic visit and will be captured for the study at the time points in the table below. Waist circumference will be measured at the level of the umbilicus at the time points reported in the table. Resting metabolic rate will be measured using expired gas analysis via the MEDGem analyzer. This will be measured following the protocol suggested by the manufacturer, including after refraining from eating, drinking, caffeine or exercise for at least 4 hours prior and immediately following a 10 minute period of quiet rest. Body fat percentage will be measured using Bioelectrical Impedance Analysis via the RJL Systems Quantum II. The Quantum II provides body fat percentage as well as a calculation of total lean mass and total fat mass.

Blood Measures

Blood will be drawn at baseline, 3 months, 6 months, 12 months, 18 months and 24 months and stored for use in later analysis.

Boxes marked with UC are tests that are done as part of usual care. Boxes marked with R are tests done for research only.

Test	BL	1m	3m	6m	9m	12m	18m	24m
Resting Metabolic Rate (MEDGem Analyzer)	UC			R		R		R
Body Fat % by Bioelectrical Impedance Analysis (RJL Systems)	UC			R		R		R
Height	UC							R
Weight	UC	UC	UC	UC	UC	UC	UC	UC
Waist Circumference	UC			R		R		R
Blood draw	R		R	R		R	R	R

Monitoring of Side Effects to study medication

Monitoring for side effects will be performed at each visit. Report of suicidal ideation will lead to study discontinuation and withdrawal from medication. Endpoint will be considered reached in this instance.

Increases in heart rate will be monitored. If > 100 beats per minute on 2 consecutive visits, participant will be withdrawn from medication and considered as endpoint reached. Metabolic acidosis will be monitored with basic metabolic panel at each follow up visit. The study clinic questionnaire will be used to monitor problems with the study drug, current dietary plan, vitals and mood changes. Any reports of abnormality on this form will be investigated further by the study physician and further action will be taken if necessary.

Depression and Suicidal Ideation

Change in mood will be assessed at each clinic visit via standard self-report questionnaire (See Clinic Questionnaire). Endorsement by participants of increased depressive symptoms will be reviewed and screened by the treatment provider at the time of the participant's appointment. Should the participant report changes in suicidal ideation, planning, or intent, the participant will be referred to the onsite Clinical Psychologist or referred to the local Emergency room for additional assessment and treatment recommendations. Participants who report significant distress associated with recent onset of mood symptoms will be provided with a list of referrals for local providers who offer counseling and psychopharmacological services. This protocol for assessment and treatment of mood symptoms is above and beyond recommended standard of care for monitoring depression and suicidal thoughts in patients taking Qsymia (topiramate) and other antiepileptic drugs (AEDs).

As a part of standard of care and consistent with guidelines published by the American Society of Metabolic Medicine, all participants will participate in psychosocial evaluation, prior to undergoing weight loss surgery. During this evaluation current/past mood symptoms and suicidal ideation/planning/intent will be assessed via self-report mood measures, a personality inventory, and via clinical interview. Participants will not be cleared to proceed with surgery if they meet criteria for a suicide attempt within the past 12 months or have active suicidal ideation, planning, or intent. Participants who are positive for these criteria will be referred for treatment; they will be reevaluated for bariatric surgery candidacy upon resolution of symptoms.

Safety Monitoring

At each physician visit (monthly during phase one and at months 1, 3, 6, 9, 12, 15, 18, and 24 during phase 2) the participant will complete an adverse events questionnaire in addition to the signs and symptoms clinic questionnaire. All adverse events will be reviewed by the study coordinator to clarify any details or questions about the reported event. The PI will then review each adverse event and determine the likelihood that the event was related to the study and whether or not it was an expected event. Study clinicians will also review the medical record at clinic visits to determine if any event or medical care occurring in the interim was related to safety and/or side effects. Any event requiring immediate reporting will be reported as such. All adverse event data will be recorded in RedCAP and tabulated every 6 months for cumulative review. The PI will be responsible for reporting cumulative frequencies of adverse events for those on study drug. Additionally, any derangements in blood

chemistries that are being monitored as part of this study will be cataloged, and frequencies will be reported for all study participants every 6 months.

Participants will be asked to bring in their pill bottles to count any remaining pills at each visit. Missed doses of medication will be noted and any excess medication will be discarded at the refill visits in the hazardous waste containers per clinic protocol. Participants will be provided with only the medication required to provide daily doses until the next scheduled clinic visit.

Some patients enrolled in the study may have diabetes and be on hypoglycemic medications or insulin prior to surgery. As part of usual care, individuals with diabetes are instructed to reduce all diabetes medication by 50% before leaving the hospital after weight loss surgery and are instructed to follow-up with their primary care provider 2 weeks after surgery in order to monitor or modify medications for diabetes and other comorbid conditions such as blood pressure. In addition, discharge documents are sent to each patient's primary care provider either through Wake One or in paper form. Prior to surgery, patients are expected to develop a relationship with a primary care provider.

Statistical analysis

This is an independent case-control study. Analyses will include completers only. Completers are defined as individuals who enter treatment and continue it (Qsymia and/or gastric sleeve) for at least 24 months without reversal or discontinuation. Participants will be recruited until the sample size of 20 cases is obtained. If a participant consents but does not have surgery, this person will not be counted as a case and thus, recruitment will continue.

Data will be entered into and stored in a REDCap database with access given only to individuals who are part of the study team. Study data uploaded will include information from the weekly clinic questionnaire, adverse events, as well as study outcomes (weight at clinic visits), demographic information, etc.

[figure not shown]
Most of the statistical analyses will be conducted using SPSS or SAS. Prior to testing the specific aims, descriptive statistics will be used to characterize the sample. Next, the groups will be compared using the chi-square statistic and T-test statistic to determine whether differences existed between the groups on key variables that may have an effect on outcomes. The case-control matching procedure should insure balance between the treatment groups on sex, age, BMI and ethnicity, but additional analyses will be used to examine the comparability between groups on baseline body composition, waist circumference, and resting metabolic rate.

The primary endpoint for this study is the proportion of patients that meet the criteria to move forward with the second surgical procedure (Roux en Y Gastric Bypass) at any point during follow up. The proportion of the Qsymia treated group that achieves the primary endpoint will be compared to the surgery only group after 24 months of follow up. Unadjusted and adjusted models will be developed to test for differences in the rate of the primary endpoint occurrence by treatment group.

The secondary outcomes for this study include percent weight loss and changes in percent body fat and resting metabolic rate. The time points of interest include pre-surgery period (baseline to surgery), baseline to 6 months (post-operative), baseline to 12 months, and baseline to 24 months. Independent T-test statistic will be used to test for differences in the changes scores between the groups at each time point for these continuous variables. Given this pilot study design and exploratory nature of this secondary aim, we will not use the conservative approach of Bonferroni adjustment for multiple comparisons. Therefore, alpha will remain at 0.05 for this family of hypotheses.

Sample size justification/statistical power

We are planning a study with 25 experimental subjects and 20 control subjects. Prior data indicate that the approximate failure rate among controls is 0.7 (Alexandrou et al, 2012). If the true failure rate for experimental subjects is 0.25, we will be able to reject the null hypothesis that the failure rates for experimental and control subjects are equal with probability (power) .840. The Type I error probability associated with this test of this null hypothesis is 0.05. We will use an uncorrected chi-squared statistic to evaluate this null hypothesis.

References

Nguyen, N et al. A review of unmet needs in obesity management. *Obes Surg.* 2012 Jun;22(6):956-66

Alexandrou et al. What is the Actual Fate of Super-Morbid-Obese Patients Who Undergo Laparoscopic Sleeve Gastrectomy as the First Step of a Two-Stage Weight-Reduction Operative Strategy? *Obes Surg* (2012) 22:1623–1628

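### Perioperative tolerability is a secondary objective, but the only stated analysis set selects on not discontinuing, so a tolerability result taken from it would look too good

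*Combined protocol and SAP*

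**What the plan says.** Secondary Objectives includes "determining tolerability of Qsymia perioperatively". The endpoint lists do not take this up. Under Statistical analysis, "The secondary outcomes for this study include percent weight loss and changes in percent body fat and resting metabolic rate", and the Secondary endpoints section likewise names only weight, body fat and resting metabolic rate. Tolerability has no measure, time window, denominator or method.

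Statistical analysis contains the only rule on who is analysed: "Analyses will include completers only". It continues: "Completers are defined as individuals who enter treatment and continue it (Qsymia and/or gastric sleeve) for at least 24 months without reversal or discontinuation". It adds that "If a participant consents but does not have surgery, this person will not be counted as a case", and that recruitment goes on until there are 20 cases.

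The text after the Exclusion Criteria says "Patients may be removed from the study at any point if they are unable to tolerate the study medication", or if they take less than half of the recommended dose.

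Safety Monitoring is a separate stream: "All adverse event data will be recorded in RedCAP and tabulated every 6 months for cumulative review", and "The PI will be responsible for reporting cumulative frequencies of adverse events for those on study drug". Laboratory derangements are to be reported for all study participants, and leftover pills are counted at each visit.

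**The concern.** Tolerability is largely a question of who cannot continue. An analysis set defined by having continued removes some or all of the people who carry that information. Three rules push the same way: the completer definition, the permitted removal of intolerant patients, and the exclusion and replacement of participants who do not reach surgery.

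The objective is also specific. Qsymia is stopped in the week before the operation and restarted in the second post-operative week (Treatment Group). How many patients cannot get through the pre-operative phase, or cannot continue after the restart, is what a pilot study should report. As written, no planned analysis returns that number, and the one stated set would make it look better than it is.

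**Working it through.** No figure in the plan bears on this point, so there is none to reproduce. The check sets the sections side by side and then gives an illustration.

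**Who leaves the analysis set**

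| Patient | Governing text | In the completer set? |
|---|---|---|
| Stops Qsymia for intolerance and is removed from the study | Text after Exclusion Criteria (removal is optional) | No |
| Stops Qsymia before surgery and never has surgery | Statistical analysis: not a case, recruitment continues | No |
| Stops Qsymia after surgery, keeps the sleeve, stays in follow-up | Completer definition, Qsymia and/or sleeve | Unclear: no if any stop of the drug disqualifies, yes if retaining the sleeve is enough |
| Takes Qsymia for 24 months apart from the planned interruption | Completer definition | Presumably yes, although the planned interruption is not expressly exempted |

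The second row also sits awkwardly with Treatment Group, which keeps patients who decline surgery on medical therapy, including Qsymia, and follows them for 2 years. They are exposed and observed but are not counted as cases.

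**Illustration.** The documents give no intolerance rate, so every rate here is an assumption. The group size of 25 is the planned experimental number in the sample size section, and 20 is the number of cases in Statistical analysis. The plan does not describe these as starters and completers. They are borrowed only as realistic sizes.

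1. Expected stops among 25 starters at assumed rates of 5%, 10%, 20% and 30%: 25 × 0.05 = 1.25, 25 × 0.10 = 2.5, 25 × 0.20 = 5, 25 × 0.30 = 7.5. If every stopper leaves the set, the set shows 0% at each of these rates.
2. Take x = 5 stops in n = 25 starters, with no other losses. The estimate is 5/25 = 20%. The exact (Clopper-Pearson) limits are the 0.025 quantile of Beta(x, n − x + 1) = Beta(5, 21), which is 0.068, and the 0.975 quantile of Beta(x + 1, n − x) = Beta(6, 20), which is 0.407. The interval is 7% to 41%.
3. If all five leave the set, the completers show 0/20. The upper limit is 1 − 0.025^(1/20) = 0.168, so the interval is 0% to 17%. That upper limit is below the 20% seen in all starters.
4. If k of the five stoppers still count as completers because they kept the sleeve, the set shows k/(20 + k): 0/20 = 0%, 1/21 = 4.8%, 2/22 = 9.1%, 3/23 = 13.0%, 4/24 = 16.7%, 5/25 = 20%. The rate is understated unless all five are kept.

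**What Safety Monitoring supplies.** It gives cumulative event frequencies for those on study drug and laboratory frequencies for all participants. It gives no count of stops over starters, no perioperative window and no link to the objective. It also leaves open whether people who have stopped the drug stay in the denominator for adverse events.

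**The case against.** The strongest reply is that the plan never says tolerability is measured in completers. The completers sentence introduces group comparisons, and historical controls took no Qsymia, so tolerability cannot be one of those comparisons. The nearest thing to a tolerability analysis is the Safety Monitoring stream, which is wider than completers: a patient who stopped in month 2 would still contribute earlier events to the cumulative tables. Removal for intolerance is permitted, not required, and the and/or in the completer definition can keep a patient who stops the drug but retains the sleeve.

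Much of this stands. A reader might infer that the tolerability population is, by construction, only those who tolerated the drug, and that the reported discontinuation rate must be zero whatever the truth. The documents do not support that. It would require every intolerant patient to be removed, the and/or to be read as and, and the safety tables to be ignored.

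The reply does not remove the problem. The completers rule is unqualified and is the only analysis-set rule in the plan, so an analyst following it literally would apply it to a stated objective. The and/or does not bring back patients removed from the study or those who never had surgery. Some withdrawals are also not optional: under Monitoring of Side Effects, reported suicidal ideation leads to study discontinuation, and a raised heart rate at two consecutive visits leads to withdrawal from medication. Those patients are counted as having reached the endpoint, yet the completers rule could drop them. The two provisions need to be reconciled.

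**Conclusion.** The point holds in limited form. Perioperative tolerability has no endpoint or analysis of its own, and the one analysis set that the plan states would bias a tolerability result towards good tolerability. Observed discontinuation would be zero if any unplanned stop of Qsymia ends completer status. It would be understated, but not necessarily zero, if some drug-stoppers who keep the sleeve are retained. Safety Monitoring lies outside the completer set and softens the problem, but it does not answer the objective.

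The size cannot be fixed from the documents. In the assumed case of 5 stops among 25 starters with no other losses, the all-treated estimate is 20% (95% CI 7% to 41%). The completer set would show between 0% (0/20, interval 0% to 17%) and 20%, depending on how many stoppers it keeps.

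**What to change.** Add to Statistical analysis: *The completers-only restriction does not apply to tolerability and safety. These are analysed in all participants who took at least one dose of Qsymia, including those who never had surgery.*

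Report the number and proportion stopping Qsymia for intolerance, with exact 95% confidence intervals, separately for the period before surgery and the period after the post-operative restart. State the denominator for each period and the length of the perioperative window. The planned stop in the week before surgery should not count as a discontinuation. Present the adverse event frequencies from Safety Monitoring alongside, and say whether participants who have stopped the drug stay in their denominator. Name this as the analysis of the tolerability objective.

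State whether a patient who stops Qsymia but keeps the sleeve is a completer, and reconcile the completer rule with the withdrawals that count as endpoint reached.

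The cost is small. Adverse events and pill counts are already collected at visits. The documents do not say that the reason for stopping is recorded, so one REDCap field is needed, plus a short extra table. No clinical rule changes.

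### Nothing in the control-matching plan keeps the choice of historical control separate from post-operative data, so it does not prevent selection on the outcome where spare matches exist

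*Combined protocol and SAP*

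**What the plan says.** The Control Group section names the source: "Control subjects for the proposed study will be identified from the patient population at the Wake Forest Baptist Health Weight Management Center". On selection it says "They will be matched to subjects in the treatment group on age, sex, ethnicity, and BMI". The controls had their operation before the study began and are found by retrospective review; no surgery-date window and no date for the matching are given.

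Statistical analysis mentions the matching once more, as a reason to expect balance: "The case-control matching procedure should insure balance between the treatment groups on sex, age, BMI and ethnicity". It does not describe the procedure. It also says "Analyses will include completers only", and defines the term: "Completers are defined as individuals who enter treatment and continue it (Qsymia and/or gastric sleeve) for at least 24 months without reversal or discontinuation". The mention of gastric sleeve with and/or suggests that the definition covers controls as well as treated patients.

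The primary endpoint depends on weight plateau, BMI and co-morbidities after surgery: "The criteria include all of the following at any point in the 24 month post-surgical follow up period". The test table marks weight as usual care at every time point.

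The text gives no age or BMI limits for a match, matching ratio, order of selection, tie-break, consecutive-patient rule, point at which the control list is locked, or selector who cannot see post-operative data.

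**The concern.** The records that supply age, sex, ethnicity and BMI for matching are held at the same centre that followed these patients after surgery. Weights are usual care, so the information that decides the primary endpoint probably sits in the same chart. Two features make it likely that this information is readable when the control set is fixed: surgery predates the study, and the completer definition appears to require someone to check 24 months of follow-up before a control counts.

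If two or three charts fit a treated patient about equally well, someone has to choose, and nothing written separates that choice from the outcome. Matching does not help, because the choice is made among candidates who already match. Good balance on the four traits is compatible with a control arm that over-represents failures. The adjusted models in Statistical analysis have no listed covariates, and adjusting for baseline traits would not undo selection on the outcome.

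At stake is the control failure rate in the primary comparison. A preference for failing charts, even an unconscious one, favours Qsymia. A preference the other way costs power.

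**Working it through.** **Inputs from the documents** (Sample size justification): control failure rate 0.70; experimental rate 0.25; type I error 0.05; uncorrected chi-squared; 25 experimental and 20 control subjects; stated power .840. Statistical analysis gives 20 cases. A two-sided test is assumed, since sidedness is not stated.

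**The plan's own figure.** Power = Φ[(d − 1.96·se₀)/se₁], with d = 0.70 − 0.25 = 0.45, se₀ from the pooled rate and se₁ from the separate rates.

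- 20 v 20: pooled rate 0.475; se₀ = √(0.475 × 0.525 × 2/20) = 0.1579; se₁ = √(0.21/20 + 0.1875/20) = 0.1410. (0.45 − 0.3095)/0.1410 = 0.997, power 0.841 (0.8405 before rounding). This matches .840.
- 25 v 20: pooled rate 0.45; se₀ = 0.1492; se₁ = 0.1342. (0.45 − 0.2925)/0.1342 = 1.174, power 0.880.

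The stated power therefore belongs to 20 v 20. The disagreement between 20 and 25 is a separate matter; both sizes are carried below.

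**Selection model** (assumed). Let r be the true failure rate and k the odds with which a failing chart is favoured over a non-failing one. The rate among selected controls is rk/(rk + 1 − r).

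- k = 1.5: 0.70 × 1.5/(1.05 + 0.30) = 1.05/1.35 = 0.778
- k = 2: 0.70 × 2/(1.40 + 0.30) = 1.40/1.70 = 0.824

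**Effect on the test.** Suppose there is no drug effect, so the treated rate is also 0.70. For every pair of counts (a failures of 20 controls, b failures of n treated), take the product of the two binomial probabilities. Sum it over the pairs where the uncorrected chi-squared test is significant and the control proportion is the higher one.

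| Selection odds | Control rate | 20 v 20 | 25 treated v 20 controls |
|---|---|---|---|
| 1 (neutral) | 0.700 | 2.7% | 2.5% |
| 1.5 | 0.778 | 8.2% | 8.6% |
| 2 | 0.824 | 14.8% | 16.2% |

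**Sensitivity to the true rate.** At 0.50 instead of 0.70, the 20 v 20 figures are 2.1%, 8.3% and 17.6%, so the size does not hinge on the 0.70.

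**Scale and direction.** One control is 1/20 = 5 percentage points of the control rate. If selection ran the other way and the control rate came out at 0.60 against a true 0.25, power would fall from 0.841 to 0.617 (20 v 20) or from 0.880 to 0.670 (25 v 20).

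**Effect of the fix.** Selecting by a fixed rule without sight of the outcome leaves the sample size and planned power unchanged. The two-sided type I error stays near nominal: at a common rate of 0.70 it is 5.3% (20 v 20) or 5.0% (25 v 20).

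**The case against.** The strongest reply is that the plan is silent on procedure and does not describe biased picking. A reader might infer that controls are to be chosen on their outcome. The documents do not support that; they show only that nothing written prevents it.

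A reader might also infer that every control's 24-month result is already visible at selection. The Control Group section requires only surgery before the study began, not 24 months before, and it does not date the matching. A control operated on shortly before the start could have an incomplete outcome when first identified. That most outcomes would be readable by the time the set is fixed is a reasonable inference, drawn from the completer definition and from matching to enrolled patients. It is not a stated fact.

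The mechanism needs surplus charts. The controls must match on four traits in a population with BMI of at least 50 kg/m² at one centre, and the documents give no pool size. If few spare matches exist, there is little discretion to misuse. This objection stands and limits what the percentages mean: the odds of 1.5 and 2 are illustrations, not estimates.

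Finally, this is a pilot study, and the gap can be closed with a few lines of text. That bears on how serious the point is, but it does not remove it: the stated objective is to demonstrate effectiveness, and the primary comparison is powered as a formal test at 0.05.

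**Conclusion.** The point holds as a gap in the written procedure. Where more than one chart could match, the plan does not prevent selection on the outcome among the controls, and neither matching nor adjustment would remove its effect. If failing charts were favoured at odds of 1.5 to 2, the chance of a false significant result for Qsymia would be about three to six and a half times its neutral value (8.2/2.7 ≈ 3.0 up to 16.2/2.5 ≈ 6.5). This assumes no drug effect, a true failure rate of 0.70, spare matching charts and a two-sided test at 0.05.

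It is also tempting to call the problem irreversible. It is not: while the charts exist, the team can list all eligible historical patients and rerun the match by a fixed rule. Settling the rule beforehand is better, because a match rerun after outcomes are known is less persuasive. The change should be made, but the point is not a fatal defect of the design.

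**What to change.** In the Control Group section, specify the following:

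1. List every historical sleeve gastrectomy patient at the centre who meets the baseline criteria within a stated surgery-date window that ends at least 24 months before selection.
2. Extract baseline fields only, preferably by someone without access to post-operative data.
3. Match by a fixed algorithm with a stated ratio, set age and BMI limits, and a tie-break.
4. Lock and date the control list, and only then extract post-operative weights, co-morbidities and any second operation.
5. State in advance that locked controls found to lack 24 months of data are reported and not replaced once outcomes are opened. Without this, the completer rule would bring back the same problem through replacement. Say in Statistical analysis how the completer rule applies to such controls.
6. Report the numbers eligible, matched and analysed.

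The cost is protocol wording, a small delay for pulling charts in two steps with the existing team, and possibly a few controls without complete follow-up. The historical-control design stays as it is.
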